2 OBJECTIVES

Specific Aim 1: To compare work productivity as measured by the Work Productivity Assessment Instrument (WPAI) after each of the 3 attacks treated with usual triptan monotherapy to each of the 3 attacks treated with Treximet.

Specific Aim 2: After 3 attacks treated with usual triptan monotherapy, and after 3 attacks treated with Treximet, to compare the Completeness of Response Survey (CORS), which will be collected and tabulated.

Specific Aim 3: To compare Migraine-ACT after usual triptan monotherapy, and Migraine-ACT after Treximet. Migraine-ACT is a validated patient-derived instrument for measuring effectiveness of acute treatment, and is particularly suited to evaluating this hypothesis because of its items on consistency of response, comfort level with treatment for planning activities, and functional evaluation:

- Consistency of response: *Does your migraine medication work consistently, in the majority of your attacks?*
- Global assessment of relief: *Does the headache pain disappear within 2 hours?*
- Impact: *Are you able to function normally within 2 hours?*
- Emotional response: *Are you comfortable enough with your medication to be able to plan your daily activities?*

Specific Aim 4: To determine if there is an interaction between medication (usual triptan vs Treximet) and patient reported pain at time of dose with respect to workplace productivity as measured by the WPAI — is one medication more effective at improving workplace productivity when migraines are more severe at time of dose?

Specific Aim 5: To compare various self-reported aspects of patient health acquired in the Knowledge Program (KP) after 3 treatments with usual triptan and 3 treatments with Treximet.

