5.2 RESCUE TREATMENT

At 2 hours post-dose, if the subject has headache pain such that additional treatment is desired, subjects treating with their Usual Triptan will be permitted to take a second dose of their Usual Triptan, or their usual care rescue medication (however, no NSAIDS or other triptans would be permitted as a rescue treatment). For subjects treating with Treximet™, who have headache pain such that additional treatment is desired at 2 hours post dose, subjects may treat with a second Treximet™tablet or their usual care rescue medication (however, no NDAIDS or other triptans would be permitted as a rescue treatment). Subjects in both treatment arms may, at 24 hours post initial dose, take a second dose tablet, (if a second dose [usual triptan or Treximet™tablet] has not already been taken),when headache pain continues to require treatment. No more than 2 Treximet™ tablets are permitted to treat one migraine.

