5.3 STUDY DRUG SUPPLY

For the treatment period when the subjects are taking Treximet™, they will be dispensed a study drug bottle containing 3 Treximet™ tablets for initial dosing (1 tablet dose) of 3 migraines during the work day.

5.3.1 Treatment Assignment will be made according to the randomization schedule created by Quantitative Health Sciences at Cleveland Clinic.

5.3.2 Treatment will be open label.

5.3.3 For study product accountability, subjects will have documented dispensation of study product and will return study drug containers at the office visit following the Treximet™ treatment arm completion.

5.3.4 Subjects will record treatment use in study diaries for the treated migraine attacks.

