6.1 EFFICACY

Efficacy comparisons of Treximet™ vs Usual Triptan treatment will be collected using the CORS 1, CORS 2, WPAI and Migraine-Act assessment tools. Pain level at time of dose is captured as part of the Study Diary.

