8.2 DESIGN AND DATA ANALYSIS CONSIDERATIONS

For the crossover design, there is a special need to identify if a carryover effect exists. For the primary outcome, WPAI score after last attack, the mean sequence sums will be compared with a 2-sample t-test (see Toutenburg in references pp. 344-346). If no significance is found, then the assumption will be that there is no carryover effect and treatment differences will be evaluated through a mixed model analysis. The model will include trial period, sequence (usual triptan f/b Treximet or Treximet f/b usual triptan) and treatment as fixed effects. If carryover does exist, then only the first trial period results will be used and a 2-sample t-test will be conducted to look for treatment differences. A sensitivity analysis will be performed in which WPAI scores from all 3 attacks will be included in the model. A second model will be created with the inclusion of an interaction term between treatment and pain level at time of dose.

Lost Workplace Productivity and Non-Work Activity Time - WPAI analysis

Subjects are to record the number of hours they miss from work due to migraine symptoms (WM), the number of hours they miss from routine activities outside of paid work due to migraine symptoms (RAM), the number of hours they continue to work while having migraine symptoms (WS), the number of hours they continue routine activities while having migraine symptoms (RAS), and how effective they are while continuing routine activities while having migraine symptoms (RAE). Lost workplace productivity (LWP) and lost activity time (LAT)

will be calculated as follows. The overall lost workplace productivity and activity time for the attack will be the sum of the two measures (LWP + LAT) where

$$LWP = WM + (WS \times [(100\% - WE)/100\%])$$

$$LAT = (RAM + (RAS \times [(100\% - RAE)/100\%]))$$

If the subject has indicated that work was not scheduled on a given diary, the LWP for that diary day will be 0 regardless of what information may have been filled out on the diary regarding WM, WS, or WE.

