APPENDIX II.5

STUDY DIARY

WEEK 1	WEEK 2
Date: ____ / ____ / ____ Day M T W TH F S SU (please circle one) Headache today Y or N (please circle one) If YES: Time Headache Started: _____ AM/PM Time Headache Stopped: _____ AM/PM Pain Level at Dose Time = _____ Scale of 0 to 10 (with 0 being absence of pain and 10 being worst possible pain)	Date: ____ / ____ / ____ Day M T W TH F S SU (please circle one) Headache today Y or N (please circle one) If YES: Time Headache Started: _____ AM/PM Time Headache Stopped: _____ AM/PM Pain Level at Dose Time = _____ Scale of 0 to 10 (with 0 being absence of pain and 10 being worst possible pain)
Date: ____ / ____ / ____ Day M T W TH F S SU (please circle one) Headache today Y or N (please circle one) If YES: Time Headache Started: _____ AM/PM Time Headache Stopped: _____ AM/PM Pain Level at Dose Time = _____ Scale of 0 to 10 (with 0 being absence of pain and 10 being worst possible pain)	Date: ____ / ____ / ____ Day M T W TH F S SU (please circle one) Headache today Y or N (please circle one) If YES: Time Headache Started: _____ AM/PM Time Headache Stopped: _____ AM/PM Pain Level at Dose Time = _____ Scale of 0 to 10 (with 0 being absence of pain and 10 being worst possible pain)
Date: ____ / ____ / ____ Day M T W TH F S SU (please circle one) Headache today Y or N (please circle one) If YES: Time Headache Started: _____ AM/PM Time Headache Stopped: _____ AM/PM Pain Level at Dose Time = _____ Scale of 0 to 10 (with 0 being absence of pain and 10 being worst possible pain)	Date: ____ / ____ / ____ Day M T W TH F S SU (please circle one) Headache today Y or N (please circle one) If YES: Time Headache Started: _____ AM/PM Time Headache Stopped: _____ AM/PM Pain Level at Dose Time = _____ Scale of 0 to 10 (with 0 being absence of pain and 10 being worst possible pain)
Date: ____ / ____ / ____ Day M T W TH F S SU (please circle one) Headache today Y or N (please circle one) If YES: Time Headache Started: _____ AM/PM Time Headache Stopped: _____ AM/PM Pain Level at Dose Time = _____ Scale of 0 to 10 (with 0 being absence of pain and 10 being worst possible pain)	Date: ____ / ____ / ____ Day M T W TH F S SU (please circle one) Headache today Y or N (please circle one) If YES: Time Headache Started: _____ AM/PM Time Headache Stopped: _____ AM/PM Pain Level at Dose Time = _____ Scale of 0 to 10 (with 0 being absence of pain and 10 being worst possible pain)

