
Date: ____ / ____ / ____
 
Day M T W TH F S SU (please circle one)
 
Headache today Y or N (please circle one)
 
If YES:
 
Time Headache Started: _____ AM/PM
 
Time Headache Stopped: _____ AM/PM
 
Pain Level at Dose Time = _____ Scale of 0 to 10 (with 0 being absence of pain and 10 being worst possible pain)
	
Date: ____ / ____ / ____
 
Day M T W TH F S SU (please circle one)
 
Headache today Y or N (please circle one)
 
If YES:
 
Time Headache Started: _____ AM/PM
 
Time Headache Stopped: _____ AM/PM
 
Pain Level at Dose Time = _____ Scale of 0 to 10 (with 0 being absence of pain and 10 being worst possible pain)

Date: ____ / ____ / ____
 
Day M T W TH F S SU (please circle one)
 
Headache today Y or N (please circle one)
	
Date: ____ / ____ / ____
 
Day M T W TH F S SU (please circle one)
 
Headache today Y or N (please circle one)

If YES: Time Headache Started: _____ AM/PM Time Headache Stopped: _____ AM/PM Pain Level at Dose Time = _____ Scale of 0 to 10 (with 0 being absence of pain and 10 being worst possible pain)	If YES: Time Headache Started: _____ AM/PM Time Headache Stopped: _____ AM/PM Pain Level at Dose Time = _____ Scale of 0 to 10 (with 0 being absence of pain and 10 being worst possible pain)
---	---

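### The diary does not tell patients to rate pain before dosing, so the Aim 4 severity score may be recalled after the outcome of a known drug

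*Combined protocol and SAP*

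**What the plan says.** Specific Aim 4 (section 2) concerns an interaction between medication and "patient reported pain at time of dose with respect to workplace productivity as measured by the WPAI". Section 8.2 carries it out: "A second model will be created with the inclusion of an interaction term between treatment and pain level at time of dose". Section 6.1 gives the source of the score: "Pain level at time of dose is captured as part of the Study Diary".

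In the diary (Appendix 11.5) every daily block from Week 1 to Week 8 has the same layout once the patient has answered that there was a headache: the time it started, then "Time Headache Stopped: _____ AM/PM Pain Level at Dose Time = _____ Scale of 0 to 10". There is one pain box per calendar day. The block has no clock time for the dose, no dose number, no drug name, and no instruction on when to enter the pain score. By contrast, the productivity questionnaire (Appendix 11.1) does state its completion time, which is bedtime on the day of treatment.

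Two other provisions matter. Section 5.3.2 states: "Treatment will be open label". Section 5.2 provides that after 2 hours "subjects treating with their Usual Triptan will be permitted to take a second dose of their Usual Triptan", with a parallel allowance for Treximet, so one attack can involve two doses.

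**The concern.** Aim 4 needs pain at dosing to be a pre-treatment characteristic of the attack. A patient who completes the block in printed order rates it after the headache has ended, knowing which drug was taken and how well it worked. Someone whose tablet failed may remember the attack as worse, and someone who did well may remember it as milder. The score then carries part of the outcome it is meant to modify.

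That alone does not create an interaction. If the distortion is equally strong under both drugs, the pain slope is biased by the same amount in each and the difference between slopes remains zero. The harm arises when recall follows outcome more strongly under one drug, which is possible when patients know what they took. A false treatment-by-severity finding could then be reported. It could not be repaired in analysis, because late and on-time entries look identical on the form.

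**Working it through.** **Inputs from the plan.** N = 60 (30 per sequence), SD of the within-patient difference 2.5, difference of 1 WPAI point, alpha 0.05 (sections 4.1 and 8.2; two-sided assumed).

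**The plan's own figure.** Noncentrality = 1/(2.5/√60) = 3.098. The noncentral t with 58 df gives power 0.861, matching the stated 86%. That figure is for the main effect; no power is stated for Aim 4.

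**Assumed inputs (not in the documents).** True pain SD 2 (variance 4), independent between periods; pain slope b = 0.3 hours per point under both drugs, so the true interaction is zero; one attack per period. An SD of difference of 2.5 implies a within-patient residual variance of 2.5²/2 = 3.125. Recorded pain = true pain + c × residual, where c is the recall shift in pain points per hour lost and may differ by drug.

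**Bias.** With patient effects removed by the crossover, for a drug with recall strength c:

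- variance of recorded pain: V(c) = 4 + 3.125c²
- fitted pain slope: S(c) = (0.3×4 + 3.125c)/V(c)
- residual variance left: R(c) = 0.09×4 + 3.125 − S(c)²V(c)

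The spurious interaction is S(c₁) − S(c₂), with standard error √{[R(c₁)+R(c₂)]/60 × [1/V(c₁)+1/V(c₂)]}.

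For 0.3 against 0:

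- S(0.3) = (1.2 + 0.9375)/4.281 = 0.499 and S(0) = 0.300, a difference of 0.199.
- R(0.3) = 2.418 and R(0) = 3.125, so SE = √{5.543/60 × (1/4.281 + 1/4)} = 0.211.
- z = 0.199/0.211 = 0.94.
- Rejection probability = Φ(0.94 − 1.96) + Φ(−0.94 − 1.96) = about 16%.

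| Recall shift by drug | Spurious slope difference | SE | False-positive rate, this formula | Range over simulations |
|---|---|---|---|---|
| equal (0.2, 0.2) | 0 | 0.208 | 5% | about 5% |
| 0.4 v 0.2 | 0.544 − 0.442 = 0.102 | 0.193 | 8% | 6–9% |
| 0.3 v 0.1 | 0.499 − 0.375 = 0.124 | 0.207 | 9% | 8–14% |
| 0.3 v 0 | 0.499 − 0.300 = 0.199 | 0.211 | 16% | about 15–30% |

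The last column comes from simulated crossovers of 60 patients with no true interaction and the pain main effect in the model. Its spread reflects a choice the documents do not settle: whether recall follows the within-patient residual (the formula above, at the low end for 0.3 v 0), the patient's whole deviation, or the hours lost. A more extreme 0.5 v 0 gives 29% by both formula and simulation.

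**Second-dose ambiguity on its own.** Suppose recall is accurate but some scores describe pain at the second dose. With 40%/40%, 50%/30% and 60%/20% of attacks affected (usual triptan/Treximet), simulated type I error was 5.0%, 5.7% and 6.8%. These shares are also assumed.

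**The case against.** Printed order is not order of completion. The blanks are separate, so a patient can enter the start time and pain when dosing and add the stop time later. The flow chart in section 6 schedules diary education and review across the study. Its content is not given, so it may or may not teach pre-dose rating. A reader might infer from the layout that the diary collects pain only after the headache has ended; the documents do not support that. What stands is that nothing in the form or in 6.1 prevents it.

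A reader might also infer that the score could just as well describe the second dose. Section 5.1 describes a single dose at headache onset, and 5.2 places later tablets under rescue, so the first dose is the natural reading. The ambiguity is real because neither the form nor 8.2 fixes the dose, but it is minor: type I error stays at about 5 to 7% in the illustration.

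Finally, the inflation depends on an assumed difference in recall between drugs, and no passage supports such a difference or its size. That objection stands as to magnitude. It does not remove the reason to close a gap that costs almost nothing to close.

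**Conclusion.** The gap is genuine and narrow. The form and section 6.1 leave open whether the Aim 4 moderator is recorded before or after the outcome, in an open-label trial where the patient knows the drug. If recall follows outcome differently by drug, the 5% interaction test could run at about 6 to 9%, 8 to 14% or 15 to 30% across the shifts examined; with equal recall it stays near 5%. These figures illustrate direction and order of size. They are not estimates for this trial, and no single value in the range should be quoted as its error rate.

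A reader might extend the point to the main result. The documents do not support that: the primary WPAI model in 8.2 contains period, sequence and treatment but no pain term, and the score does not enter the Migraine-ACT or CORS analyses. This is a cheap improvement to one secondary aim. It is separate from the absence of a treatment-use field on the diary (promised in 5.3.4), because adding that field would not make the pain rating a pre-dose one.

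**What to change.** Make pain the first item after the headache question is answered yes, worded: 'Pain level just before your FIRST dose for this headache (write this down before taking the tablet), 0 to 10.' Repeat the instruction in section 6.1 so that diary education covers it. In section 8.2, state that the model with "inclusion of an interaction term between treatment and pain level at time of dose" uses only the first-dose rating.

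The cost is a revised paper form, one added sentence in each of 6.1 and 8.2, and slightly more burden on the patient at dosing. It needs no extra visits, patients or data items, and changes no dosing or rescue rule.

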APPENDIX 11.6

TREXIMET™ PACKAGE INSERT

HIGHLIGHTS OF PRESCRIBING INFORMATION

These highlights do not include all the information needed to use TREXIMET safely and effectively. See full prescribing information for TREXIMET.

TREXIMET (sumatriptan and naproxen sodium) tablets, for oral use
Initial U.S. Approval: 2008

WARNING: CARDIOVASCULAR AND GASTROINTESTINAL RISKS	
See full prescribing information for complete boxed warning.	
• Nonsteroidal anti-inflammatory drugs (NSAIDs) cause an increased risk of serious cardiovascular thrombotic events, myocardial infarction, and stroke, which can be fatal. This risk may increase with duration of use. Patients with cardiovascular disease or risk factors for cardiovascular disease may be at greater risk. (5.1)	
• NSAIDs cause an increased risk of serious gastrointestinal adverse events including bleeding, ulceration, and perforation of the stomach or intestines, which can be fatal. These events can occur at any time during use and without warning symptoms. Elderly patients are at greater risk for serious gastrointestinal events. (5.2)	

RECENT MAJOR CHANGES	
Indications and Usage (1)	05/2015
Dosage and Administration (2.2)	05/2015

INDICATIONS AND USAGE

TREXIMET is a combination of sumatriptan, a serotonin (5-HT₁) receptor agonist (triptan), and naproxen sodium, a non-steroidal anti-inflammatory drug, indicated for the acute treatment of migraine with or without aura in adults and pediatric patients 12 years of age and older. (1)

Limitations of Use:

- Use only if a clear diagnosis of migraine headache has been established. (1)
- Not indicated for the prophylactic therapy of migraine attacks. (1)
- Not indicated for the treatment of cluster headache. (1)

DOSAGE AND ADMINISTRATION

Adults:

- Recommended dosage: 1 tablet of 85/500 mg. (2.1)
- Maximum dosage in a 24-hour period: 2 tablets of 85/500 mg; separate doses by at least 2 hours. (2.1)

Pediatric Patients 12 to 17 years of Age:

- Recommended dosage: 1 tablet of 10/60 mg. (2.2)
- Maximum dosage in a 24-hour period: 1 tablet of 85/500 mg.

Mild to Moderate Hepatic Impairment:

- Recommended dosage: 1 tablet of 10/60 mg. (2.3, 8.7)

DOSE FORMS AND STRENGTHS

Tablets: 85 mg sumatriptan / 500 mg naproxen sodium (3)
10 mg sumatriptan / 60 mg naproxen sodium (3)

CONTRAINDICATIONS

- History of coronary artery disease or coronary vasospasm. (4)
- History of coronary artery bypass graft surgery. (4)
- Wolff-Parkinson-White syndrome or other cardiac accessory conduction pathway disorders. (4)
- History of stroke, transient ischemic attack, or hemiplegic or basilar migraine. (4)
- Peripheral vascular disease. (4)
- Ischemic bowel disease. (4)
- Uncontrolled hypertension. (4)

FULL PRESCRIBING INFORMATION: CONTENTS*

- 1 INDICATIONS AND USAGE
- 2 DOSAGE AND ADMINISTRATION
 - 2.1 Dosage in Adults
 - 2.2 Dosage in Pediatric Patients 12 to 17 years of age
 - 2.3 Dosage in Patients with Hepatic Impairment
 - 2.4 Administration Information
- 3 DOSAGE FORMS AND STRENGTHS
- 4 CONTRAINDICATIONS
- 5 WARNINGS AND PRECAUTIONS
 - 5.1 Myocardial Ischemia, Myocardial Infarction, Stroke, Prinzmetal's Angina
 - 5.2 Gastrointestinal Bleeding, Ulceration, and Perforation

- Recent (within 24 hours) use of another 5-HT₁ agonist (e.g., another triptan) or of ergotamine-containing medication. (4)
- Concurrent or recent (past 2 weeks) use of monoamine oxidase-A inhibitor. (4)
- Asthma, rhinitis, and nasal polyps syndrome induced by aspirin or other NSAID/analgesic drugs. (4)
- Hypersensitivity to sumatriptan, naproxen, or any other component of TREXIMET (angioedema and anaphylaxis seen). (4)
- Third trimester of pregnancy. (4)
- Severe hepatic impairment. (4)

WARNINGS and PRECAUTIONS

- Myocardial ischemia/infarction, stroke, Prinzmetal's angina: Perform cardiac evaluation in patients with cardiovascular risk factors. (5.1)
- Arrhythmias: Discontinue TREXIMET if occurs. (5.3)
- Chest/throat/neck/jaw pain, tightness, pressure, or heaviness: Generally not associated with myocardial ischemia; evaluate for coronary artery disease in patients at high risk. (5.4)
- Cerebral hemorrhage, subarachnoid hemorrhage, and stroke: Discontinue TREXIMET if occurs. (5.5)
- Gastrointestinal ischemic reactions and peripheral vasospastic reactions: Discontinue TREXIMET if occurs. (5.6)
- Hypertension: Monitor blood pressure. (5.7)
- Heart failure and edema: Use with caution in patients with fluid retention or heart failure. (5.8)
- Medication overuse headache: Detoxification may be necessary. (5.9)
- Serotonin syndrome: Discontinue TREXIMET if occurs. (5.10)
- Renal papillary necrosis and other renal injury with long-term use: Discontinue TREXIMET if occurs. (5.11)
- Anaphylactic reactions: TREXIMET should not be given to patients with the aspirin triad. (5.12)
- Serious skin reactions: Discontinue TREXIMET at first sign of rash. (5.13)
- Elevated liver enzymes and severe hepatic reactions: Discontinue use immediately if abnormal liver enzymes persist or worsen. (5.15)

ADVERSE REACTIONS

The most common adverse reactions (incidence ≥2%) were:

- Adults: Dizziness, somnolence, nausea, chest discomfort/heart pain, neck/throat/jaw pain/tightness/pressure, paresthesia, dyspnea, dry mouth. (6.1)
- Pediatrics: Hot flush (i.e., hot flash(es)) and muscle tightness. (6.1)

To report SUSPECTED ADVERSE REACTIONS, contact Pernix Therapeutics at [name] or FDA at [name] or www.fda.gov/medwatch.

DRUG INTERACTIONS

- Methotrexate: Increases methotrexate plasma levels. (7.4)
- Aspirin: Use not recommended. (7.5)
- Angiotensin-converting enzyme inhibitors, diuretics, beta-blockers: May reduce antihypertensive effects. (7.7)
- Lithium: Increases lithium plasma levels. (7.9)
- Warfarin: Higher risk of serious gastrointestinal bleeding. (7.12)

USE IN SPECIFIC POPULATIONS

- Pregnancy: Based on animal data, may cause fetal harm. (8.1)
- Severe Renal impairment: Not recommended in patients with creatinine clearance <30 mL/min. (8.6)

See 17 for PATIENT COUNSELING INFORMATION and FDA-approved Medication Guide.

Revised: 05/2015

- 5.3 Arrhythmias
- 5.4 Chest, Throat, Neck, and/or Jaw Pain/Tightness/Pressure
- 5.5 Cerebrovascular Events
- 5.6 Other Vasospasm Reactions
- 5.7 Hypertension
- 5.8 Congestive Heart Failure and Edema
- 5.9 Medication Overuse Headache
- 5.10 Serotonin Syndromes
- 5.11 Renal Toxicity
- 5.12 Anaphylactic Reactions
- 5.13 Serious Skin Reactions
- 5.14 Pregnancy
- 5.15 Hepatotoxicity

5.16	Hematologic Toxicity	8.2	Labor and Delivery
5.17	Exacerbation Asthma Related to Aspirin Sensitivity	8.3	Nursing Mothers
5.18	Seizures	8.4	Pediatric Use
6	ADVERSE REACTIONS	8.5	Geniatric Use
6.1	Clinical Trials Experience	8.6	Renal Impairment
7	DRUG INTERACTIONS	8.7	Hepatic Impairment
7.1	Ergot-Containing Drugs	10	OVERDOSAGE
7.2	Monoamine Oxidase-A Inhibitors	11	DESCRIPTION
7.3	Other 5-HT ₁ Agonists	12	CLINICAL PHARMACOLOGY
7.4	Methotrexate	12.1	Mechanism of Action
7.5	Aspirin	12.2	Pharmacodynamics
7.6	Selective Serotonin Reuptake Inhibitors/Serotonin Norepinephrine Reuptake Inhibitors and Serotonin Syndromes	12.3	Pharmacokinetics
7.7	Angiotensin-Converting Enzyme Inhibitors	13	NONCLINICAL TOXICOLOGY
7.8	Diuretics	13.1	Carcinogenesis, Mutagenesis, Impairment of Fertility
7.9	Lithium	13.2	Animal Toxicology and/or Pharmacology
7.10	Probenecid	14	CLINICAL STUDIES
7.11	Propranolol and Other Beta-Blockers	14.1	Adults
7.12	Warfarin	14.2	Pediatric Patients 12 to 17 Years of Age
7.13	Drug/Laboratory Test Interactions	16	HOW SUPPLIED/STORAGE AND HANDLING
8	USE IN SPECIFIC POPULATIONS	17	PATIENT COUNSELING INFORMATION
8.1	Pregnancy	*Sections or subsections omitted from the full prescribing information are not listed.	

FULL PRESCRIBING INFORMATION

WARNING: CARDIOVASCULAR AND GASTROINTESTINAL RISKS

- **Cardiovascular Risk:** Nonsteroidal anti-inflammatory drugs (NSAIDs) cause an increased risk of serious cardiovascular thrombotic events, myocardial infarction, and stroke, which can be fatal. This risk may increase with duration of use. Patients with cardiovascular disease or risk factors for cardiovascular disease may be at greater risk [see *Warnings and Precautions (5.1)*].
- **Gastrointestinal Risk:** NSAIDs cause an increased risk of serious gastrointestinal adverse events including bleeding, ulceration, and perforation of the stomach or intestines, which can be fatal. These events can occur at any time during use and without warning symptoms. Elderly patients are at greater risk for serious gastrointestinal events [see *Warnings and Precautions (5.2)*].

